5.13.10 Sunitinib or Cabozantinib Dosing-Delay Criteria

Sunitinib or cabozantinib dosing should be delayed for the following:

- If UPCR ≥ 2.0 [≥ 227 mg/mmol] urine dipstick protein $\geq 3+$, obtain 24-hour urine protein to determine if dosing should be delayed.
 - Dosing may proceed if 24-hour urine protein < 3 g.
 - Delay dosing if 24-hour urine protein ≥ 3 g (see Section 5.13.11 for criteria to resume).
 - Recurrent 24-hour urine protein ≥ 3 g after dose reduction requires study drug discontinuation (refer to Sections 5.14.1.2 and 5.14.1.3).
- Clinical manifestations of CHF
- LVEF $> 20\%$ but $< 50\%$ below baseline
- Any Grade 2 drug-related hemorrhage
- Any Grade 2 or 3 drug-related venous thrombosis requiring anticoagulation, with the following exception:
 - Any recurrent or worsening venous thromboembolic event after restarting sunitinib or cabozantinib will require discontinuation
- Any Grade 3 drug-related adverse event or Grade 3 drug-related laboratory abnormality (e.g., AST, ALT, total bilirubin) that persists for more than 1 week or worsens despite supportive care management, with the following exceptions:
 - Grade ≥ 2 drug-related arterial thromboembolic events, including cerebrovascular ischemia, cardiac ischemia, or peripheral or visceral arterial ischemia, require discontinuation.
 - Grade ≥ 3 drug-related hemorrhage requires discontinuation (Section 5.14.1.2).
 - Drug-related AST or ALT $> 8 \times$ ULN requires discontinuation (Section 5.14.1.2).

- Concurrent AST or ALT $> 3 \times$ ULN ($> 2 \times$ baseline AND $> 3 \times$ ULN for patients with baseline elevation) and total bilirubin $> 2 \times$ ULN ($> 2 \times$ baseline AND $> 2 \times$ ULN for patients with baseline elevation), consistent with potential drug-induced liver injury (see Section 8.10), requires discontinuation.
- Grade 3 drug-related amylase or lipase abnormalities that are not associated with symptoms or clinical manifestations of pancreatitis do not require dose delay. In such cases, more frequent monitoring (e.g., weekly) of amylase and lipase is recommended. If amylase or lipase worsens to Grade 4 severity or the patient develops symptoms or clinical manifestations of pancreatitis, dosing should be delayed.

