5.13.12.2 Cabozantinib

Reduce the starting dose of cabozantinib to 40 mg once daily in patients with moderate hepatic impairment (i.e., Child-Pugh Class B); refer to the cabozantinib (Cabometyx[®]) US Prescribing Information and/or the corresponding SmPC for updated dosing guidance or further information. For patients receiving a concomitant strong CYP3A4 inducer or inhibitor, follow the dosing guidelines in the Package Insert, SmPC, or local health authority guidelines applicable to your country.

Dose reductions for adverse event management are allowed for cabozantinib (Table 7). Cabozantinib doses will not be re-escalated once reduced, unless a concomitant strong CYP3A4 inducer is started (see Section 5.13.12.3); however, escalation above the starting dose is not allowed.

After toxicity requiring a dose delay has improved and meets the criteria to resume dosing (Section 5.13.11), patients who were receiving cabozantinib 40 mg daily prior to the delay will resume cabozantinib at 20 mg daily. If more than 2 dose reductions are necessary (i.e., reduction to less than 20 mg daily) or more than 1 dose reduction in patients with Child-Pugh Class B (i.e., starting dose 40 mg daily), cabozantinib must be permanently discontinued (Section 5.14.1.3).

Patients who required a dose delay due to 24-hour urine protein ≥ 3 g, may resume study treatment at a reduced dose once UPCr is < 2 [< 227 mg/mmol]. Recurrent 24-hour urine protein ≥ 3 g after dose reduction requires study drug discontinuation (refer to Section 5.14.1.3).

Patients who required a dose delay due to Grade 3 hypertension, which improved with antihypertensive medications, or any Grade 2 or 3 drug-related adverse event or asymptomatic laboratory abnormality that improved to Grade ≤ 1 within 7 days with supportive medical care may resume cabozantinib at the same dose or a reduced dose, at the discretion of the Investigator.

Patients with asymptomatic Grade 2 drug-related AST, ALT or total bilirubin elevation, or Grade 3 drug-related lipase or amylase abnormalities that are not associated with symptoms or clinical manifestations of pancreatitis may reduce cabozantinib by 1 dose level, without delaying dosing, at the discretion of the Investigator.

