 - ◆ Treatment-emergent ALT or AST > 3 times ULN ($> 2 \times$ baseline AND $> 3 \times$ ULN for patients with baseline elevation) AND
 - ◆ Total bilirubin > 2 times ULN ($> 2 \times$ baseline AND $> 2 \times$ ULN for patients with baseline elevation) or clinical jaundice, without initial findings of cholestasis (e.g., elevated serum alkaline phosphatase) (see Section 8.10)

In most cases of Grade 3 AST or ALT elevation that do not improve with hepatic AE management, study treatment will be permanently discontinued (see Section 5.13 for more details). If the Investigator determines a possible favorable benefit/risk ratio that warrants continuation of study treatment, a discussion between the Investigator and the Medical Monitor must occur. For IL-2 mediated ALT/AST elevations $< 8.0 \times \text{ULN}$ in Cycle 1 only, study treatment does not need to be discontinued.

- Any Grade 4 drug-related adverse event or laboratory abnormality (including but not limited to creatinine, AST, ALT, or total bilirubin), except for the following events which do not require discontinuation:
 - Grade 4 neutropenia ≤ 7 days
 - Grade 4 lymphopenia or leukopenia or asymptomatic amylase or lipase
 - Isolated Grade 4 electrolyte imbalances/abnormalities that are not associated with clinical sequelae and are corrected with supplementation/appropriate management within 72 hours of their onset
 - Grade 4 drug-related endocrinopathy adverse events (except adrenal insufficiency or hypophysitis), such as, hyper- or hypothyroidism, or glucose intolerance, which resolve or are adequately controlled with physiologic hormone replacement (corticosteroids, thyroid hormones) or glucose-controlling agents, respectively, may not require discontinuation after discussion with and approval from the Medical Monitor.
 - Note: For Grade ≥ 3 adrenal insufficiency and/or Grade ≥ 4 hypophysitis, treatment needs to be discontinued regardless of control with hormone replacement (hospitalization for diagnostic workup of adrenal insufficiency without severe symptoms should not require discontinuation).
- Any event that leads to delay in dosing lasting > 8 weeks from the previous dose requires discontinuation, with the following exceptions:

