5.14.1.2 Sunitinib Discontinuation Criteria

Treatment with sunitinib should be permanently discontinued for any of the following:

- Any requirement for more than 2 sunitinib dose reductions
- Any Grade drug-related arterial thrombosis
- Grade ≥ 3 drug-related hemorrhage or recurrent Grade 3 drug-related hemorrhage after dose reduction
- Grade 4 drug-related symptomatic venous thrombosis
- LVEF reduction $\geq 50\%$ from baseline
- Grade 4 drug-related cardiac toxicity
- Any other Grade ≥ 2 drug-related arterial or venous thromboembolic events including cerebrovascular ischemia, cardiac ischemia, or peripheral or visceral arterial ischemia
- Erythema multiforme, Stevens-Johnson syndrome, toxic epidermal necrolysis or necrotizing fasciitis
- Thrombotic microangiopathy
- Nephrotic syndrome or repeat episodes of urine protein ≥ 3 g despite dose reductions
- Angioedema due to hypersensitivity
- Two or more symptomatic episodes of hypertension despite modification of antihypertensive medication(s) and reduction of sunitinib dose
- Any drug-related LFT abnormality that meets the following criteria require discontinuation:
 - Treatment-emergent ALT or AST > 3 times ULN ($> 2 \times$ baseline AND $> 3 \times$ ULN for patients with baseline elevation)
 - Total bilirubin > 2 times ULN ($> 2 \times$ baseline AND $> 2 \times$ ULN for patients with baseline elevation) or clinical jaundice, without initial findings of cholestasis (e.g., elevated serum alkaline phosphatase) (see Section 8.10)
 - Sunitinib should be interrupted for Grade 3 or 4 drug-related hepatic adverse reactions and discontinued if there is no resolution within 7 days. Sunitinib should be permanently discontinued if a patient subsequently experiences Grade 3 or 4 changes in LFT or have other signs and symptoms of liver failure.
- Any dosing delay lasting > 8 weeks unless the Medical Monitor is consulted and agrees with the rationale for resuming therapy after a delay > 8 weeks. Note that tumor assessments should continue as per protocol even if dosing is delayed.
- Any adverse event, laboratory abnormality, or intercurrent illness which, in the judgment of the Investigator, presents a substantial clinical risk to the patient with continued sunitinib dosing.

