5.14.1.3 Cabozantinib Discontinuation Criteria

Permanently discontinue cabozantinib for patients with any of the following:

- Any requirement for more than 2 cabozantinib dose reductions (i.e., reduction to less than 20 mg)
- Acute myocardial infarction or new CVA event (including TIA) confirmed by imaging (DWI MRI preferred; refer to [Appendix 6](#))
- Any other Grade ≥ 2 drug-related arterial or venous thromboembolic events including cerebrovascular ischemia, cardiac ischemia, or peripheral or visceral arterial ischemia
- LVEF reduction $\geq 50\%$ from baseline
- Any Grade ≥ 3 hemorrhage
- Grade 4 hypertension or persistent Grade 3 hypertension despite optimal medical management and cabozantinib dose reduction
- Reversible posterior leukoencephalopathy syndrome
- Development of GI perforation or drug-related fistula
- Nephrotic syndrome or recurrent nephrotic range proteinuria (i.e., recurrent 24-hour urine protein ≥ 3 g after dose reduction)
- Any drug-related LFT abnormality that meets the following criteria requires discontinuation:
 - Treatment-emergent ALT or AST > 3 times ULN ($> 2 \times$ baseline AND $> 3 \times$ ULN for patients with baseline elevation)
 - Total bilirubin > 2 times ULN ($> 2 \times$ baseline AND $> 2 \times$ ULN for patients with baseline elevation) or clinical jaundice, without initial findings of cholestasis (e.g., elevated serum alkaline phosphatase) (see Section [8.10](#))
- Any Grade 4 drug-related adverse event or laboratory abnormality, with the following exceptions:
 - Grade 4 neutropenia ≤ 7 days
 - Grade 4 lymphopenia or leukopenia
 - Grade 4 amylase or lipase abnormalities that are not associated with symptoms or clinical manifestations of pancreatitis
 - Isolated Grade 4 electrolyte abnormalities that are not associated with clinical sequelae and are corrected with supplementation/appropriate management within 72 hours of their onset
- Any dosing delay lasting > 8 weeks unless the Medical Monitor is consulted and agrees with the rationale for resuming therapy after a delay > 8 weeks. Note that tumor assessments should continue as per protocol even if dosing is delayed.

- Any adverse event, laboratory abnormality, or intercurrent illness which, in the judgment of the Investigator, presents a substantial clinical risk to the patient with continued cabozantinib dosing.

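### The sunitinib and cabozantinib liver stopping lists do not say whether the transaminase and bilirubin conditions are joint, and some conflicts with the dose-delay section remain on either reading

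*Protocol*

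**What the plan says.** Section 5.14.1 makes the drug-specific lists mandatory, and both TKI lists are headed as applying when any one of their items is met.

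- **Sunitinib (5.14.1.2).** The liver item reads "Any drug-related LFT abnormality that meets the following criteria require discontinuation". Its first sub-bullet is "Treatment-emergent ALT or AST > 3 times ULN", with a variant for raised baseline values. The second is total bilirubin above 2 times ULN or clinical jaundice, without initial cholestasis. The third is a full instruction: "Sunitinib should be interrupted for Grade 3 or 4 drug-related hepatic adverse reactions and discontinued if there is no resolution within 7 days".
- **Cabozantinib (5.14.1.3).** "Any drug-related LFT abnormality that meets the following criteria requires discontinuation", followed by the same first two sub-bullets and no third.
- **Arm A (5.14.1.1).** The same transaminase item ends with an explicit connector: "ULN for patients with baseline elevation) AND".
- **Dose delay, both TKIs (5.13.10).** Dosing is delayed for "Any Grade 3 drug-related adverse event or Grade 3 drug-related laboratory abnormality (e.g., AST, ALT, total bilirubin) that persists for more than 1 week" or that worsens despite supportive care. Among the exceptions, drug-related AST or ALT above 8 times ULN requires discontinuation, citing 5.14.1.2. Concurrent AST/ALT above 3 times ULN and bilirubin above 2 times ULN is described as "consistent with potential drug-induced liver injury (see Section 8.10), requires discontinuation".
- **Dose reduction.** Under 5.13.12.2, a patient with an asymptomatic Grade 2 AST, ALT or bilirubin elevation "may reduce cabozantinib by 1 dose level, without delaying dosing". Under 5.13.12.1, sunitinib may resume after a Grade 2 or 3 laboratory abnormality that improves to Grade 1 or lower within 7 days.

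**The concern.** These are stopping rules that sites must follow, and the text allows two readings of the same laboratory result. Two sites could both follow the protocol, with one permanently stopping a TKI and the other reducing or briefly holding it.

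The missing connector affects only the control arm of an open-label trial. Earlier TKI discontinuation could bring forward subsequent therapy. Under SAP 7.5.1.1 that closes the window for best overall response, and under SAP 7.5.2.1 it censors PFS. SAP 7.2 also counts patients who met withdrawal criteria and were not withdrawn as important protocol deviations, and that review needs an unambiguous criterion.

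**Working it through.** No sample size, power or alpha is involved, so the check compares the texts.

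**Step 1. How the two liver conditions are connected**

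| Section | Applies to | Link between ALT/AST > 3x ULN and bilirubin > 2x ULN |
|---|---|---|
| 5.14.1.1 | Arm A | explicit AND |
| 8.13 (potential DILI) | all patients | explicit AND |
| 5.13.10 | both TKIs | must be concurrent |
| 5.14.1.2 | sunitinib | none |
| 5.14.1.3 | cabozantinib | none |

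**Step 2. Suppose each bullet is a separate trigger.** ALT/AST above 3 times ULN alone then ends TKI treatment. This clashes with:

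- 5.13.10, both drugs. Its Grade 3 delay rule could never operate for AST/ALT, and its 8 times ULN and concurrent-bilirubin criteria would be redundant.
- 5.13.12.1, sunitinib. A patient with a Grade 2 or 3 abnormality that settles within 7 days may resume there, but would already have been stopped.
- 5.13.12.2, cabozantinib only. Grade 2 AST/ALT may be handled by one dose-level reduction.
- The third sunitinib bullet, which interrupts for Grade 3 or 4 hepatic reactions and stops only if they have not resolved in 7 days.

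The documents do not print the CTCAE grade limits. The clash with 5.13.12.2 assumes that values just above 3 times ULN are Grade 2. Section 5.13.3 is consistent with this: for ALT/AST above 3.0 and up to 5.0 times ULN it waits for resolution to Grade 1 or baseline, so that range lies above Grade 1. The clashes with the Grade 3 rules assume that Grade 3 also lies above 3 times ULN.

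**Step 3. Suppose the first two bullets are joint.** The clashes in step 2 disappear, because isolated transaminase elevation no longer triggers the list. The cause of those clashes is therefore the missing connector.

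**Step 4. What a joint reading leaves.**

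1. Section 5.13.10 cites 5.14.1.2 for discontinuation above 8 times ULN. That threshold appears in neither 5.14.1.2 nor 5.14.1.3.
2. For a sunitinib patient with Grade 3 AST/ALT persisting beyond one week, 5.13.10 calls for a delay. The third bullet of 5.14.1.2 interrupts at Grade 3 and calls for discontinuation once 7 days pass without resolution. The same patient on day 8 is to be delayed under one section and permanently stopped under the other.
3. The TKI lists refer to Section 8.10 for liver injury (5.13.10 and 5.14.1.1 do too). Section 8.10 covers immune-mediated events; the potential DILI definition is in 8.13.

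**The case against.** The strongest reply is that this is one missing word with an obvious meaning. The liver sub-lists refer to meeting the following criteria, whereas one level up the drafters wrote that any item suffices. Section 5.13.10 uses the same thresholds for the same drugs and requires concurrence. The qualifier about cholestasis also appears in the two AND-joined versions. The third sunitinib bullet is an instruction rather than a criterion, so it does not prevent the first two from being joint; it would make little sense if 3 times ULN alone already ended treatment.

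Most of this stands: the joint reading fits the rest of the protocol better. It does not dispose of the point, because the list itself does not state that reading and the three defects in step 4 survive it.

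A reader might also infer that control patients are stopped for changes that Arm A patients continue through. The documents do not support that. Section 5.13.2 delays nivolumab for Grade 2 drug-related AST, ALT or bilirubin abnormalities and requires its discontinuation at Grade 3 or above, outside the Cycle 1 exception. Section 5.13.3 delays treatment in Cycle 1 above 3 times ULN. Section 5.13.7 asks for return to baseline before dosing resumes after Grade 2 values.

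**Conclusion.** The concern holds as an internal inconsistency. The sunitinib and cabozantinib lists are ambiguous on whether the two liver conditions are joint. The separate-trigger reading contradicts three other sections and the sunitinib list itself, and the joint reading still leaves an unmatched 8 times ULN rule, a delay-versus-stop conflict for sunitinib, and wrong cross-references.

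A reader might go further and conclude that the protocol, as written, ends TKI treatment on any isolated transaminase above 3 times ULN. The wording permits that reading but does not establish it, and 5.13.10 points the other way.

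The size cannot be stated. The patients exposed to the ambiguity are those in Arm B with an isolated transaminase above 3 times ULN or an isolated bilirubin above 2 times ULN, and the documents give no frequency. Shorter control-arm exposure is possible but not shown. Discontinuing treatment does not end tumor assessment or survival follow-up (5.6, 5.14.1), and OS is analyzed as randomized. The Grade 2 and Grade 3 parts of the argument rest on the assumptions in step 2.

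**What to change.** Reconcile 5.13.10, 5.13.12, 5.14.1.2, 5.14.1.3 and 8.13 so that they give one consistent rule for each TKI. The revised text should state:

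- whether the transaminase and bilirubin conditions are joint or separate;
- whether an 8 times ULN rule applies and, if so, to which drug and in which section;
- how the Grade 3 delay rule in 5.13.10 relates to the 7-day rule in 5.14.1.2;
- the correct section for the DILI definition wherever 8.10 is now cited for it.

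The sponsor's medical team decides which rule stands; this review takes no position on that. The cost is a protocol clarification or amendment, with no additional patients or data.

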- Sustained Grade 3 drug-related hypertension (systolic blood pressure ≥ 160 mm Hg or diastolic blood pressure ≥ 100 mm Hg). Note: Stopping or reducing the dose of sunitinib or cabozantinib is expected to cause a decrease in blood pressure. The treating physician should monitor the patient for hypotension and adjust the number and dose of antihypertensive medications accordingly.
- Grade 4 drug-related amylase or lipase abnormalities require dose delay. Patients should be monitored for development of symptoms or clinical manifestations of pancreatitis.
- Grade 4 drug-related electrolyte abnormalities require dose delay. Electrolyte correction with supplementation/appropriate management should be promptly initiated.
- Grade 4 drug-related neutropenia, lymphopenia, leukopenia, anemia, or thrombocytopenia
- Any adverse event, laboratory abnormality, or intercurrent illness which, in the judgment of the Investigator, warrants delaying sunitinib or cabozantinib dosing
- For patients scheduled for major surgery, including dental surgery which may impact bone healing, sunitinib or cabozantinib dosing should be delayed at least 28 days prior to scheduled surgery. The treating physician should use clinical judgment with regard to the risks and benefits of the planned surgical procedure if it is not possible to delay cabozantinib or sunitinib dosing for 28 days prior to the procedure. A delay of cabozantinib and sunitinib dosing of 5 to 7 days is recommended for healing for minor surgery.

As a general approach, all AEs related to sunitinib or cabozantinib should be managed with supportive care, when possible, at the earliest signs of toxicity. Calcium, magnesium, potassium, and phosphorus should be kept above the lower limits of the laboratory normal values. Please refer to the sunitinib or cabozantinib prescribing information for additional information regarding dose modifications and AE management.

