5.13.12.1 Sunitinib

Sunitinib dose reductions are permitted as per the approved product label for safety reasons or when a concomitant strong cytochrome P450 3A4 (CYP3A4) inhibitor is needed (Appendix 8). Selection of an alternative concomitant medication with minimal or no enzyme inhibition potential is recommended whenever possible.

After toxicity requiring a dose delay has improved and meets the criteria to resume dosing (Section 5.13.11), patients should resume sunitinib at one dose level reduction. Dose reductions

should occur in 12.5 mg decrements. No more than 2 dose reductions are allowed. If more than two dose reductions are necessary (i.e., reduction to less than 25 mg daily), the patient must be permanently discontinued (Section 5.14.1.2).

Patients who required a dose delay due to Grade 3 hypertension, which improved with antihypertensive medications, or any Grade 2 or 3 drug-related adverse event or asymptomatic laboratory abnormality that improved to Grade \leq 1 within 7 days with supportive medical care may resume sunitinib at the same dose or a reduced dose, at the discretion of the Investigator.

Patients who required a dose delay due to 24-hour urine protein \geq 3 g, may resume study treatment at a reduced dose once UPCR is $<$ 2 ($<$ 227 mg/mmol). Repeat episodes of urine protein \geq 3 g despite dose reductions require study drug discontinuation (refer to Section 5.14.1.2).

At the time a dose reduction is considered, also refer to Section 5.13.10 for dose delay recommendations and Section 5.14 for discontinuation criteria.

Sunitinib dose re-escalations are permitted as per the approved product label when a concomitant CYP3A4 inducer is needed (Appendix 8); however, escalation above the starting dose is not allowed. Selection of an alternative concomitant medication with minimal or no enzyme induction potential is recommended whenever possible.

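### Sunitinib liver rules differ between the dosing-delay and discontinuation sections, and the AST/ALT > 8 x ULN stop cites a list that does not contain it

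*Protocol*

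**What the plan says.** Section 5.13.10 (dosing delay, both TKIs) has one trigger line for Grade 3 toxicity judged drug-related. It covers adverse events as well as laboratory values, and its laboratory part reads "Grade 3 drug-related laboratory abnormality (e.g., AST, ALT, total bilirubin) that persists for more than 1 week or worsens despite supportive care management". Two liver exceptions to that line call for discontinuation. One is for drug-related AST or ALT above 8 x ULN; its wording ends "ULN requires discontinuation (Section 5.14.1.2". The other is concurrent ALT/AST above 3 x ULN with bilirubin above 2 x ULN. The section also allows a delay for any event that, "in the judgment of the Investigator, warrants delaying sunitinib or cabozantinib dosing", and tells sites to "refer to the sunitinib or cabozantinib prescribing information for additional information regarding dose modifications and AE management".

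Section 5.14.1.2 (sunitinib discontinuation) has a bullet on drug-related liver function test (LFT) abnormalities with three sub-items: ALT or AST above 3 x ULN; bilirubin above 2 x ULN or jaundice; and "Sunitinib should be interrupted for Grade 3 or 4 drug-related hepatic adverse reactions and discontinued if there is no resolution within 7 days". The third goes on to require a permanent stop "if a patient subsequently experiences Grade 3 or 4 changes in LFT". The figure 8 x ULN does not appear in this section.

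Section 5.13.12.1 says that a patient delayed for a Grade 2 or 3 drug-related event or asymptomatic laboratory abnormality that improved to Grade 1 or less "within 7 days with supportive medical care may resume sunitinib at the same dose or a reduced dose", at the investigator's discretion.

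**The concern.** Section 5.13 sends a site to its own subsections for when to hold a drug and to Section 5.14 for when to stop it. For sunitinib liver toxicity, each rule is partly in the other place. The immediate hold is in the stop list, and the > 8 x ULN stop is in the hold list.

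A site working from 5.13.10 could keep dosing through a stable Grade 3 liver rise that 5.14.1.2 says to interrupt. A site that looks up the > 8 x ULN stop in 5.14.1.2 finds an interrupt-first line and no such stop, and could hold and later restart. At stake are the safety of sunitinib patients and uniform handling of holds across sites.

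**Working it through.** No formula applies. The check is to set the two sections side by side, case by case.

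| Drug-related liver finding on sunitinib | 5.13.10 | 5.14.1.2 |
|---|---|---|
| Isolated Grade 3 laboratory rise, AST/ALT at or below 8 x ULN, stable, first week | No delay required | Interrupt, no waiting period |
| Same rise, unresolved beyond the week | Delay starts | Discontinue if unresolved within 7 days |
| AST or ALT above 8 x ULN | Discontinue, citing 5.14.1.2 | No such item; Grade 3 or 4 is interrupted first |
| ALT/AST above 3 x ULN together with bilirubin above 2 x ULN | Discontinue | Discontinue |

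**First and second rows.** The triggers differ if the hepatic reactions in 5.14.1.2 include laboratory rises. Two features of the text support that. The line sits under the LFT bullet, and its next sentence speaks of a later Grade 3 or 4 LFT change. The sequel differs as well. Once 5.13.10 has started a delay, 5.13.11 allows resumption at Grade 1 or less or baseline, with no hepatic exception and no 7-day limit. Under 5.14.1.2, a rise interrupted at onset and unresolved after 7 days ends sunitinib permanently.

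**Third row.** The cross-reference does not resolve. Neighbouring citations in 5.13.10 do: Grade 3 or higher hemorrhage and repeat urine protein of 3 g or more both appear in 5.14.1.2. From 5.14.1.2 alone, a rise above 8 x ULN that resolves within 7 days is not barred from restart, and 5.13.12.1 would then allow the same or a reduced dose after a Grade 3 event. Section 5.13.10 bars that restart.

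**Assumption in the third and fourth rows.** The ALT/AST and bilirubin sub-items of 5.14.1.2 are read as joined. The matching item in 5.14.1.1 ends "ULN for patients with baseline elevation) AND", but 5.14.1.2 prints no such word. If the two were separate criteria, ALT or AST above 3 x ULN alone would stop sunitinib and the > 8 x ULN gap would close.

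**Size.** A dose count is not a useful measure. More than 1 week leaves the seventh day after detection still permitted, so a rise found on Cycle 1 Day 8 could see dosing on Days 8 to 15, which is 15 - 8 + 1 = 8 doses. It could equally be none, because the investigator may hold at any time. The documents give neither a Grade 3-4 hepatic rate for this trial nor a planned sunitinib share of Arm B, so the number of patients affected cannot be derived.

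**The case against.** The strongest reply is that the sections are linked and can be followed together. Section 5.13.10 cites 5.14.1.2 on the AST/ALT > 8 x ULN line itself, so a reader checking a liver rise is sent to the section that holds the interruption rule. Section 5.13 says at the outset that drug must be discontinued as Section 5.14 requires. Section 5.13.12.1 refers to both sections when a dose reduction is considered. Investigators may hold earlier on judgment, and the prescribing information is cited. All of this stands, and it makes the practical effect modest. It does not remove the inconsistency: 5.13.10 neither restates the immediate-interruption rule nor defers to it, and an investigator's option to hold is not a requirement to hold.

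A second reply is that the first case depends on reading. Section 8.1 makes a laboratory value an adverse event only if the investigator finds it clinically significant. If a Grade 3 rise counts as an adverse event, and the 1-week qualifier in 5.13.10 applies only to laboratory abnormalities, both sections hold at once. If it is not an adverse event, one can argue that 5.14.1.2 does not apply. The LFT bullet and the sentence after the interruption line favour the reading used here but do not settle it. That two careful readers could differ is itself a reason to clarify.

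A reader might infer that no site can comply with both sections. The documents do not support this, since 5.13.10 never forbids an earlier hold. Nor is the > 8 x ULN stop absent from the protocol: 5.13.10 states it for both TKIs.

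**Conclusion.** The point holds as an inconsistency in safety instructions. For an isolated Grade 3 drug-related liver laboratory rise with AST/ALT at or below 8 x ULN, the delay section sets a later trigger than the discontinuation section. For AST/ALT above 8 x ULN, the delay section cites a stop that the cited list does not contain.

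This rests on two readings: that the hepatic line of 5.14.1.2 covers laboratory rises, and that its ALT/AST and bilirubin items are joined. The effect is on sunitinib handling in Arm B only and is modest, because the stricter rule satisfies both sections. Nothing in the documents supports extending it to the endpoints, alpha or power. It is worth correcting because these are hold-or-stop rules for liver toxicity, and sites should not have to reconcile two sections to find them.

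**What to change.** In 5.13.10, add a sunitinib exception to the Grade 3 line:
- Grade 3 or 4 drug-related hepatic adverse reactions or LFT abnormalities require immediate interruption, and permanent discontinuation if not resolved within 7 days, with a pointer to 5.14.1.2.
- Resolved means Grade 1 or less or baseline, as in 5.13.11. The present text leaves the word undefined although it decides a permanent stop.
- AST or ALT above 8 x ULN, or the concurrent ALT/AST and bilirubin criterion, requires immediate permanent discontinuation instead.

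In 5.14.1.2, add drug-related AST or ALT above 8 x ULN as a discontinuation item exempt from the interrupt-first line. Print AND between the ALT/AST > 3 x ULN and bilirubin items, as in 5.14.1.1. Keep the existing stop for recurrent Grade 3 or 4 LFT changes. Section 5.13.12.1 can stay as it is.

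The cost is amendment text with IRB/IEC approval under Section 11.1, which can go into the next amendment, and slightly more early sunitinib holds. No extra procedures are needed.
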